Stimulation effects on sexual arousal are unlikely to be observed in the clinic. If this study is successful, future proposals to investigate underlying mechanisms may evaluate in vivo effects with animal models. We will have subjects complete four standard surveys as has been done for other

[figure not shown]

Figure 1. Study paradigm. Subjects will be randomized into one of two test groups (DGNS/PTNS). Sexual Function and Quality of Life surveys will be taken at study initiation and at 6-week intervals afterwards. The final 6-week period of no stimulation will look for long-term carry over.

neuromodulation studies [1], [6], [10-12]. The Female Sexual Function Index (FSFI) is a standardized survey with 19 questions on sexual health that provides a maximum score of 36 [13] (See Appendix 1 for survey). The short form 36-question (SF-36) quality of life survey was designed for general use in clinical practice [14] and will be used here to assess overall impact (See Appendix 2 for survey). The Measure of Symptoms - American Urological Association Symptom Index is a standardized 8-question survey assessing urologic concerns. The Patients' Global Impression of Change (PGIC) Scale is a 1-question survey designed to assess patients' feelings of improvement after intervention. Subjects will take the four surveys before study initiation (baseline), after each of concurrent 6-week stimulation sessions in the clinic (6weeks; 12weeks), and six weeks after study completion (long-term).

Due to the relatively small sample sizes planned for this study, we will use non-parametric statistical testing. We will use a two-sided Wilcoxon rank sum test to make comparisons of the survey scores among the different subject groups [1], [6], [8], [15], with a significance level of 0.05. FSFI and SF-36 scores will be compared for each of the potential comparisons among the baseline, 6-week and 12-week study time points and at long-term time point, for DGNS and PTNS groups separately.

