We plan for a total study size of 30 subjects. 15 subjects will be assigned to each stimulation group – DGNS and PTNS. As this is a pilot study that has not been performed before, we do not have an effect size from which to calculate a target sample size. This study size of 15 subjects for each stimulation approach was selected for two reasons. Our primary factor was that prior pilot studies using these stimulation approaches for other patient groups used similar study sizes of 9-10 subjects [3-4], [8-9]. Our secondary factor was that given the one-year time frame of our planned study, larger sample sizes may not be feasible. If one or both stimulation approaches are successful, larger sample sizes will be performed in subsequent studies.

[figure not shown]

Figure 2. DGNS electrode locations. For experimental DGNS, the TENS unit will be connected to electrodes placed on either side of the clitoris.

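### The pilot gives its lack of an effect size as the reason for having no sample size calculation, yet plans only tests at 0.05 and does not commit to reporting a change, its SD or an interval

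*Combined protocol and SAP*

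**What the plan says.** All of this is in the Combined protocol and SAP.

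- **Sample size** (Description of methods and analysis): "We plan for a total study size of 30 subjects", and "15 subjects will be assigned to each stimulation group". No calculation is given because "we do not have an effect size from which to calculate a target sample size". Two reasons are offered instead. The main one is that "prior pilot studies using these stimulation approaches for other patient groups used similar study sizes of 9-10 subjects"; the second is that a larger sample may not be feasible within the one-year time frame.
- **Next step** (same section): "If one or both stimulation approaches are successful, larger sample sizes will be performed in subsequent studies". Success is not defined.
- **Analysis** (same section): "We will use a two-sided Wilcoxon rank sum test to make comparisons of the survey scores among the different subject groups", "with a significance level of 0.05". The plan then specifies that "FSFI and SF-36 scores will be compared for each of the potential comparisons among the baseline, 6-week and 12-week study time points", with the long-term time point added and the two arms handled separately.
- **Collection, analysis and interpretation of results**: total scores will be compared across time points as already described, sub-sections may be compared if the data suggest trends, and a statistical consultant will be met to confirm approaches and conclusions.

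None of these places names an estimate of change, an SD of change, a confidence interval or a between-arm difference in change as something to be reported.

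**The concern.** What a later trial needs from this pilot is what the pilot says it lacks: a plausible size of change and, above all, its variability. A p-value from 15 women gives neither. It also does not separate an approach with no useful effect from one whose effect the test missed.

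The only numerical criterion attached to any result is 0.05, and the step to larger studies depends on an undefined notion of success. If success came to be judged by significance, a real moderate effect would be missed more often than found, and the effects that did pass would look larger than they are. The one comparison that randomisation protects, DGNS against PTNS in change from baseline, has no planned estimate. The sentence on comparing subject groups could be read as including a between-arm test, but the specification that follows it is within each arm.

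**Working it through.** **Inputs from the documents:** 15 per arm, two arms, total 15 + 15 = 30, which agrees with the stated total; two-sided 0.05. The documents give no effect size, SD, power or dropout rate, so no formula can reproduce the sample size.

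**Assumptions:** results are in units of the SD of change; changes are normally distributed; true changes range from 0.2 to 1.0 SD. The within-arm comparison is taken as paired (Wilcoxon signed-rank), because the same women are measured at each time point. The protocol names the rank sum test, so these figures describe a paired version of the planned comparison.

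**Step 1. Power, and overstatement if only significant results count.** For n = 15 the exact two-sided signed-rank test rejects when the smaller rank sum is 25 or less (actual level 0.048). Simulation, 40,000 runs per row:

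| Assumed true change (SD) | Power | Mean estimate in significant positive results ÷ truth | Mean estimate (SD) |
|---|---|---|---|
| 0.2 | 10% | 3.05 | 0.2 × 3.05 = 0.61 |
| 0.3 | 18% | 2.14 | 0.3 × 2.14 = 0.64 |
| 0.5 | 42% | 1.44 | 0.5 × 1.44 = 0.72 |
| 0.8 | 80% | 1.10 | 0.8 × 1.10 = 0.88 |
| 1.0 | 94% | 1.03 | 1.0 × 1.03 = 1.03 |

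Separate runs gave 17–18% at 0.3 SD and 41–42% at 0.5 SD. The third column applies only if significance is the filter.

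**Step 2. Precision if estimates were reported.** 95% half-widths, with the SD of change taken as equal in both arms:

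- Within an arm: t(0.975, 14)/√15 = 2.145/3.873 = 0.55 SD.
- Between arms: t(0.975, 28) × √(2/15) = 2.048 × 0.365 = 0.75 SD.
- If 12 per arm complete (an assumed figure): t(0.975, 11)/√12 = 0.64 SD, and t(0.975, 22) × √(2/12) = 0.85 SD.

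The within-arm half-width is also roughly the observed change needed for significance on a paired t-test. This is why a true change of 0.3 or 0.5 SD reaches significance mainly when chance pushes the estimate up.

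**Step 3. Precision of the SD.** The 95% limits for the true SD, as multiples of the observed SD, are √[14/χ²(0.975, 14)] = 0.73 and √[14/χ²(0.025, 14)] = 1.58. Required sample size scales with the square of the SD, so at the upper limit a later trial would need about 1.58² ≈ 2.5 times the number implied by the observed SD. The pilot can supply an SD, but later planning has to allow for that uncertainty.

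**The case against.** The strongest reply has four parts.

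1. **The information is not lost.** FSFI and SF-36 are scored at four time points for each woman, so changes and SDs can be computed, and a consultant will be involved. This stands. A reader might infer that the pilot cannot yield an effect size, but the documents do not support that. The gap is a missing commitment to report, and the consultation does not say what will be reported.
2. **No rule ties success to p<0.05.** This also stands. A reader might infer that the plan will advance only significant results, or will size the next trial on the change observed. The documents say neither, and they describe the controlled study as following a demonstration of feasibility. The overstatement figures are therefore conditional, and they are small (3–10%) at true changes of 0.8 to 1.0 SD.
3. **The size of 15 has an open rationale.** Precedent and the one-year time frame are reasonable grounds for a pilot, and nothing here argues for a different number.
4. **The plan does not equate non-significance with persistence.** A reader might infer that a non-significant change between week 12 and the long-term survey would be taken as lasting benefit. The plan never says so, and comparing every pair of time points also covers long-term against baseline.

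What remains is that the reported outputs, as written, do not include the quantities the next trial would be planned from.

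**Conclusion.** The point holds as a gap in what the plan commits to report. Having cited a missing effect size, it names only tests at 0.05, and neither a per-arm change with its SD and interval nor the DGNS-PTNS difference in change.

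Significance at 15 per arm is a weak guide to success: power is about 18%, 41% and 80% at assumed true changes of 0.3, 0.5 and 0.8 SD. If it were used as the success rule, the observed change would average about 2.1, 1.4 and 1.1 times the truth. These figures rest on normal changes, a paired test and complete data.

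One limit applies even after correction. There is no control stimulation, so a within-arm change, however well estimated, is not an effect against control and should not be entered as the between-arm difference in a later controlled trial. The change is worth making before any data are seen.

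**What to change.** **Description of methods and analysis, statistical paragraph.** Make estimation the main result for FSFI and SF-36:

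- per arm, the paired change as a Hodges-Lehmann estimate with 95% CI, and the SD of change, for 12-week minus baseline, long-term minus baseline, and long-term minus 12-week;
- the DGNS-PTNS difference in change, with 95% CI;
- p-values as supporting information.

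**Same section, sample size paragraph.** Keep 15 per arm and both existing reasons. Add the expected precision (about ±0.55 SD within an arm and ±0.75 SD between arms, with complete data). State that later planning will use the intervals and SDs, allowing for their imprecision, and not whether p was below 0.05. Note that an uncontrolled within-arm change is not an effect against control.

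**Cost.** A few sentences and minor programming, with no additional participants or data. The small downside is that the stated precision will look modest.

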### Potential difficulties

We anticipate several potential difficulties with these planned studies. Patient compliance may be an issue, as the need to visit the clinic for 12 consecutive weeks may be a burden. We may adjust the study budget (or draw from [name] startup funds) to allocate funds to pay for daily parking (~\$7) and to give a lump sum upon completion of the study (\$50) to each subject. As other PTNS studies use weekly study durations, sometimes with much larger sample sizes, we expect that a similar willingness will occur here.

It is possible that patients find the planned stimulation amplitudes (e.g.  $PA_T$  or  $2 \times PA_T$ ) to be uncomfortable. As it is not our goal to explore optimal stimulation parameters here, we will keep current levels as low as necessary to maintain subject comfort.

It is possible that transient genital arousal or pain may occur in the clinic directly as a result of the applied electrical

[figure not shown]

Figure 3. Electrode setup for PTNS. For experimental PTNS, the TENS unit will be connected to electrodes, on either side of the ankle. Figure modified from [6].

stimulation. To protect subject privacy and modesty, we will ensure that subjects are located in private rooms and left alone for the duration of applied stimulation. Subjects will be given a method to report uncomfortable side effects if they should occur. At the conclusion of each session, we will survey subjects as to any transient pain or arousal to compare effects over time.

It is possible that patients attending [name] clinic do not have intercourse frequently enough to be eligible for the study ( $\geq 1$  time per month). If we observe that occurrence through the first month of recruitment (3 clinics) then we will relax the criteria to be a desire to have intercourse several times per month. Conversely, it is possible that subjects who have intercourse 1-2 times a month may not provide sufficient perspective on the efficacy of the stimulation for improving arousal. We will observe for this potential trend during the first 5-10 patients and will adjust the inclusion criteria threshold upwards as necessary.

It is possible that patients may develop psychological discomfort during the research intervention. To reduce this risk, patients will be fully informed about the treatment regimen, such as the fact that they may have a doctor placing leads on their genitals every week. They will also be reminded that their continued participation is voluntary. If psychological trauma is raised, patients will be referred to our sexual health therapists for treatment. [name] is a registered nurse and sexual health therapist who does such therapy and is part of the study team.

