### Recruitment and retention

Potential subjects will be recruited from an investigator’s clinic or related clinics. Only inclusion/exclusion criteria that are provided by the patient as part of their check-in procedures or prior visits will be used to make a decision to approach a potential study subject. If a patient expresses interest in the study, then eligibility based on the full inclusion/exclusion criteria list will be verified.

The study coordinator/nurse will follow up with the patient to schedule the stimulation sessions and will administer the baseline surveys (American Urological Association Symptom Index - AUA, Female Sexual Function Index – FSFI, Short Form Health Survey – SF-36) via mail or email. Informed consent will be obtained in person at the first stimulation session, prior to any intervention. After each session, the coordinator will remind subjects of subsequent meetings.

Patient personal information will be protected per HIPAA guidelines.

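### Staff ask about stimulation-related pain and arousal only as each session ends, and only as transient effects, so delayed or persisting reactions are not systematically collected

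*Combined protocol and SAP*

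**What the plan says.** All references are to the combined protocol and SAP.

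*Potential difficulties* names the reaction: "It is possible that transient genital arousal or pain may occur in the clinic directly as a result of the applied electrical" stimulation. Two ways of learning about it follow. One is initiated by the subject: "Subjects will be given a method to report uncomfortable side effects if they should occur". This comes directly after the text on leaving her alone in a private room during stimulation. The other is asked by staff: "At the conclusion of each session, we will survey subjects as to any transient pain or arousal to compare effects over time". The same section separately foresees discomfort from the stimulation amplitude, and later psychological discomfort, for which referral is offered.

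*Description of methods and analysis* schedules four questionnaires (FSFI, SF-36, the AUA symptom index and PGIC) at baseline, 6 weeks, 12 weeks and six weeks after the end. *Collection, analysis and interpretation of results* places the 6-week forms before the 7th session and the 12-week forms after the 12th. The last set is obtained by phone or mail. That section compares total scores over time and leaves sub-sections optional, to be examined if the data suggest a trend.

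**The concern.** A question put as the woman leaves can record what she has felt so far. It cannot record pain that starts later that day, or show how long a reaction lasted once she went home. If no one asks at the next visit, such a reaction reaches the data only if she raises it herself.

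This matters because the trial is a pilot, and *Description of methods and analysis* says larger studies will follow if an approach succeeds. A low count of reactions from this trial could partly reflect when the question was asked. Recruitment is mainly from a pelvic pain clinic, and *Population characteristics* describes patients with dyspareunia and pelvic or bladder pain. Without onset and duration, a flare after stimulation cannot be told apart from background pain.

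**Working it through.** The plan states no figure on this point, so there is none to reproduce. The check sets each collection route against what would be needed, then counts the intervals.

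**Inputs**
- 12 weekly sessions (*Potential difficulties*; *Collection, analysis and interpretation of results*).
- 15 women per arm, 30 in total (*Description of methods and analysis*).
- Questionnaires after baseline at 6 weeks, 12 weeks and six weeks after the end (same section).
- FSFI-6 items with a four-week recall (*Inclusion criteria*). The 19-item FSFI is in an appendix that was not available.

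**Routes compared**

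| Route | Asked by staff? | About reactions to stimulation? | Covers the time after she leaves? |
|---|---|---|---|
| Session-end survey | Yes, 12 times | Yes | Not as described: transient effects, asked at session end |
| Side-effect reporting route | No, she must start it | Yes | No window stated |
| FSFI | Yes, 3 times after baseline | No, judging by the FSFI-6 items | In part |
| SF-36, AUA index, PGIC | Yes, 3 times after baseline | Not described as such | Not stated |

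No row has a clear yes in all three columns.

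**Intervals without a staff-asked reaction question**
- Between 12 sessions: 12 − 1 = 11 intervals.
- After session 12: 1 period of six weeks.
- Per woman: 11 + 1 = 12 intervals. Per arm: 15 × 12 = 180. Whole trial: 30 × 12 = 360.

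These are opportunities to ask, not missed events. The documents give no rate of delayed reactions, so the number missed cannot be calculated.

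**How far the FSFI reaches**
- Nominal duration: 12 + 6 = 18 weeks.
- If the full FSFI has the four-week recall of the FSFI-6 (assumption), three surveys look back over 3 × 4 = 12 of 18 weeks.
- If the recall were six weeks or more, they would cover all 18.

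The conclusion is the same at both ends of this range, because the limit is content rather than calendar time. The FSFI-6 items shown ask about arousal in sexual activity and pain on penetration. A total score gives no onset, no duration and no link to a session.

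**The case against.** The strongest reply is that the survey sits where the named risk is expected. *Potential difficulties* speaks of a transient reaction in the clinic, and the plan asks about it there. No section raises later or lasting reactions. Women also have a reporting route with no stated time limit, the FSFI asks about pain and arousal at three later points, and a team member sees each woman weekly to place electrodes. The coordinator is in touch as well: "After each session, the coordinator will remind subjects of subsequent meetings". Adverse event procedures could be in the consent pages or appendices.

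Much of this stands. A reader might infer that these reactions go uncounted altogether. The documents do not support that: a woman can volunteer a report, and the FSFI may pick up some change. They support only that collection is not systematic. Nor do they show that staff would be unaware of a reaction before the next session. Weekly contact exists; what is missing is a scripted question. The coordinator's contact is described as a scheduling reminder.

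A reader might also see a contradiction with the statement that "Stimulation effects on sexual arousal are unlikely to be observed in the clinic". That sentence introduces the questionnaires used to measure benefit. It does not concern adverse reactions, so it does not conflict with expecting transient pain or arousal in the clinic.

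Finally, pain and arousal are not the only physical effects foreseen, since discomfort from the amplitude is named too. The exact items of the session-end survey are not given, so its reach is judged from its timing and from the word transient.

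**Conclusion.** The point holds in a limited form. Staff solicit stimulation-related pain and arousal only at session end and only as transient effects. The supplied text has no staff-asked question about reactions in any of the 12 intervals per woman (11 between sessions, one after the last). Delayed or persisting reactions are not systematically collected, and the pilot could understate them.

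The size of any understatement is unknown. No planned comparison of questionnaire scores is affected, and the trial's validity for those comparisons is not in question.

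The conclusion rests on two assumptions: that the full FSFI resembles the FSFI-6 in content, and that the pages and appendices not available contain no further side-effect collection. If they do contain it, the protocol should refer to it and the point falls away.

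**What to change.** In *Potential difficulties*, keep the session-end survey. Add the same pain and arousal items, worded to cover the time since the last session, with onset and duration. Ask them before stimulation at sessions 2 to 12 (11 times). Ask them once more at the six-week post-trial contact already planned in *Collection, analysis and interpretation of results*. That fills all 11 + 1 = 12 intervals without a new visit. If a session is missed, the wording covers the longer gap when the woman next attends.

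Report by arm the number of women with in-session reactions and the number with between-session reactions. Because background pain is common in this population and there is no control stimulation, present these as descriptive counts with their timing, not as reactions proven to be caused by stimulation.

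This is a change to data collection only. It sets no rule for how stimulation should respond to the answers.

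The cost is protocol wording, two or three questions, a few minutes per visit, and probably a higher reported reaction count than the present plan would give.

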## Recruitment & Retention Plan

### Population characteristics

The proposal involves a 30-subject prospective study of surface electrode stimulation (dorsal genital nerve or posterior tibial nerve) weekly sessions for improving sexual arousal. As described below, adult women over the age of 18 who are neurologically stable and have intercourse at least once a month will be candidates. Typical patients will likely be in excess of 40 years of age. During each stimulation session, subjects will be reclined in a chair or examination table and will have electrodes placed at the appropriate location. After setting of parameters, stimulation will be applied for 30 minutes in duration.

We will be recruiting patients primarily from [name] pelvic pain clinic as described below. The characteristics of the patients include dyspareunia (pain with intercourse), and/or pelvic or bladder pain. The bulk of [name] pain in this clinic (~5 new patients each session, plus similar numbers of return visits) have pain with intercourse and pelvic pain as major components of their complaints. There is a sexual health therapist present in the clinic who sees most of the new patients, so we will have a psychosocial evaluation for many of them.

Patients will also be recruited from the OB/GYN clinic, other sex therapists' clinics, and UHS.

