### Inclusion criteria

- Adult women  $\geq 18$  years of age
- Sexually active  $\geq 1$  time per month ( $\geq 2$  times per month preferred)
- Having sexual dysfunction as identified by a score of 19 or less on the FSFI-6 [16].

For each question: Over the past four weeks...						
How would you rate your level (degree) of sexual desire?		Very high (5)	High (4)	Moderate (3)	Low (2)	Very low or none at all (1)
How would you rate your level of sexual arousal ("turn on") during sexual activity or intercourse?	No sexual activity (0)	Very high (5)	High (4)	Moderate (3)	Low (2)	Very low or none at all (1)
How often did you become lubricated ("wet") during sexual activity or intercourse?	No sexual activity (0)	Almost always or always (5)	Most times (4)	Sometimes (3)	A few times (2)	Almost never or never (1)
When you had sexual stimulation or intercourse, how often did you reach orgasm?	No sexual activity (0)	Almost always or always (5)	Most times (4)	Sometimes (3)	A few times (2)	Almost never or never (1)

How satisfied have you been with your overall sexual life?	Very satisfied (5)	Mod-erately satisfied (4)	About equally satisfied and dissatisfied (3)	Mod-erately dissatisfied (2)	Very dissatisfied (1)	
How often did you experience discomfort or pain during vaginal penetration?	Did not attempt intercourse (0)	Almost never or never (5)	A few times (4)	Some-times (3)	Most times (2)	Almost always or always (1)

- Neurologically stable
- Ambulatory
- Capable of giving informed consent
- English speaking
- Capable and willing to follow study procedures

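### If the activity criterion is relaxed to desire alone, FSFI-6 of 19 or less cannot exclude a woman inactive for four weeks; the upward change has a window but no threshold

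*Combined protocol and SAP*

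**What the plan says.** Inclusion criteria asks for sexual activity at least once per month (twice preferred) and, as the only listed test of dysfunction, "Having sexual dysfunction as identified by a score of 19 or less on the FSFI-6". The FSFI-6 table printed there is headed "For each question: Over the past four weeks". Its arousal, lubrication and orgasm items each have a response for no sexual activity that scores 0. Its pain item has a response for no attempted intercourse that also scores 0. The desire and satisfaction items run from 1 to 5 with no zero option.

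Potential difficulties provides for two changes to the activity criterion.

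- **Downward.** If intercourse proves too infrequent over the first month of recruitment (3 clinics), "we will relax the criteria to be a desire to have intercourse several times per month". No matching change to the FSFI-6 rule is given.
- **Upward.** Women having intercourse 1 to 2 times a month "may not provide sufficient perspective on the efficacy of the stimulation for improving arousal". The plan continues: "We will observe for this potential trend during the first 5-10 patients and will adjust the inclusion criteria threshold upwards as necessary".

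Population characteristics says that most patients in the main recruiting clinic "have pain with intercourse and pelvic pain as major components of their complaints".

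**The concern.** The two inclusion rules work together. Recent activity is what lets four of the six FSFI-6 items measure function. Replace activity with desire, leave the cutoff alone, and an inactive woman passes the dysfunction test whatever her underlying function. The trial would then report a population with FSFI-6-identified dysfunction that includes women for whom the score showed nothing of the kind.

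The upward change raises a different question. Its stated reason is how well low-frequency subjects can inform on efficacy, judged in patients already being treated. The plan names no measure, threshold, new value or decision-maker. Post-treatment data will exist by then: Potential difficulties provides for an arousal and pain survey after every session, and Description of methods and analysis repeats the FSFI from 6 weeks. If those data enter the decision, later eligibility could follow early impressions of response.

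**Working it through.** The documents give no FSFI-6 range or derived figure on this point, so there is nothing to reproduce. The inputs are the response options in the Inclusion criteria table, the cutoff of 19, and the planned total of 30 (Description of methods and analysis).

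**1. No activity and no attempted intercourse in four weeks.**
Total = desire (1–5) + satisfaction (1–5) + 0 + 0 + 0 + 0 = 2 to 10.
Distance from the cutoff: 19 − 10 = 9 points at the least.
Of the 5 × 5 = 25 possible answer patterns, none exceeds 19. If the relaxed criterion implies desire of at least low (2–5), the range is 3 to 10 and the conclusion is the same.

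**2. Women for whom the rule still works.** The counts below are answer patterns, not probabilities.

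| Past four weeks | Items scored 1–5 | Range | Patterns above 19 |
|---|---|---|---|
| Active, intercourse attempted | 6 | 6–30 | 5,251 of 15,625 |
| Active, intercourse not attempted | 5 (pain = 0) | 5–25 | 247 of 3,125 |
| Inactive, not attempted | 2 | 2–10 | 0 of 25 |

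The gap is therefore confined to the last row.

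**3. Illustration.** Take a woman with desire 4 and each of the four activity-dependent items at 4. Her total is 4 + 4 × 4 + satisfaction (1–5) = 21 to 25, so she is excluded. After four inactive weeks, with desire still 4, it is 4 + satisfaction (1–5) = 5 to 9, so she is included. This holds at every satisfaction level.

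**4. Upward change.** The observation window is 5/30 = 17% to 10/30 = 33% of the planned sample. This is the size of the window, not of any bias.

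**The case against.** The strongest reply is that the relaxation is conditional. The operative criteria still require activity, and the relaxed rule applies only if the first month goes badly. Even then it affects only women inactive in every scored respect for four weeks. In a pelvic pain clinic, four inactive weeks may be part of the dysfunction, and no passage suggests that well-functioning inactive women would enrol in number. All of this stands. It limits the consequence but does not change what the score can show for these women.

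On the upward change, the text asks whether reports from low-frequency subjects are informative, not whether those subjects improve, and it does state a window. Description of methods and analysis also says that effects on arousal are unlikely to be seen in the clinic, which weakens the per-session survey as a source of early efficacy signals. A reader might infer that eligibility will be adapted to observed response, but the documents do not say so. What remains is that no threshold is given and no post-treatment data are ruled out.

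A reader might also infer that inactive women who resume activity would gain FSFI points artificially, so that the uncontrolled within-group comparisons are biased upward. The documents do not establish this. The FSFI-6 is used only for eligibility. The outcome is the 19-item FSFI, whose scoring is in an appendix not in the text reviewed. Resumed activity could also be genuine benefit.

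**Conclusion.** Two limited points hold.

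First, if the relaxation is used, the unchanged FSFI-6 rule cannot exclude any woman with no sexual activity and no attempted intercourse in the past four weeks. Her total is 2 to 10 against a cutoff of 19. This is exact from the protocol's own form. It means that the rule does not establish dysfunction in these women, not that they lack it. Their number cannot be derived from the documents, and no size is claimed for any effect on the outcome.

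Second, the upward change is left open. It has a window of 5 to 10 of 30 patients, but no threshold or new value, and nothing keeps post-treatment reports out of the decision.

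Both are worth settling before either change is used. Neither undermines the pilot as a whole.

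**What to change.** (a) If the relaxation is used, flag at screening the women whose FSFI-6 zeros come from inactivity. Report their number, and do not describe them as having FSFI-6-identified dysfunction. Dropping the zero items from the sum would not help, because the total stays 2 to 10. Applying the cutoff to an earlier active period is not advised either, because it takes the form outside its four-week window and no document supports the cutoff there.

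(b) Keep the as-scored FSFI as the main analysis and report the number of zero-activity answers at each visit. If Appendix 1 scores inactivity as 0 (an assumption here), add a descriptive sensitivity analysis, either without the flagged women or in women active at both compared visits. The second version depends on post-baseline behaviour and should be labelled so. The first uses only a screening flag.

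(c) Base any upward change only on baseline activity frequency, with the trigger and the new value written down in advance. Make the decision without sight of FSFI change or the per-session arousal answers. Keep everyone already randomised in the analysis.

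The cost is some eligibility and analysis wording, one screening flag and one extra descriptive analysis. The downsides are small subsets (at most 15 per group) and less freedom to adjust eligibility during recruitment.
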